9.6. Secondary Endpoint Analyses

There are no secondary endpoints to be analyzed.

9.7. Additional Analyses

Three different Speech in Noise (SIN) test lists will be administered at clinic visit 2 (unaided) and again at clinic visit 3 (aided). The three lists were specifically chosen based on their homogeneity and as such, average test scores will be computed as the average of the test scores from the three lists. Average test scores and test scores from each of the three lists will be summarized descriptively for each assessment visit for each of the two randomized groups (Self-Fit and Pro-Fit) along with corresponding 95% confidence intervals for the means based on the t-distribution. Additionally, the mean difference between treatment groups of the within-subject differences (clinic visit 3 – clinic visit 2) will be reported along with the corresponding two-sided 95% confidence interval.

For the real ear measures (REM) testing, the REM output values (dB SPL) will be summarized descriptively from all available ears at each frequency (0.25, 0.5, 1, 2, 3, 4, 6, and 8 kHz) and averaged across all frequencies separately for each of the two study arms (Self-Fit and Pro-Fit) for each of the two clinic visits. These REM analyses will be

performed separately at 50, 65, and 80 dB SPL. The mean absolute difference (MAD) between the Self-Fit and NAL-NL2 targets and the MAD between the Pro-Fit and NAL-NL2 targets will also be computed for each clinic visit at each frequency (0.5, 1, 2, and 4 kHz) and averaged across all frequencies using all available ears. Two-sided 95% bootstrap confidence intervals (sampling subjects with replacement) for the MAD values will also be reported.

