2.3. Study Objectives

2.3.1. Primary Objective

Primary Objective	Procedure Measures
Assess subjective non-inferiority in user -perceived benefit between a Self-Fitted (tuned) hearing assist settings group and a Professionally-Fitted (tuned) hearing assist settings group in participants with perceived or measured mild to moderate hearing loss.	Clinic Visit 1 Following enrollment, participants will be randomly assigned into 2 independent groups (SF or PF). The software enabled hearing aid algorithm will be used in SF group, and the audiologist best practice algorithm will direct baseline hearing aid settings in PF group.

	
Home Interval 1
 
During daily activities, participants will observe strengths and weaknesses of their hearing aid settings to guide/inform subsequent fine-tuning in clinic. Participants have the option to make setting adjustments during this interval for listening needs and/or to avoid discomfort.
 
Clinic Visit 2
 
Real Ear measures will follow fine-tuning in both groups. Specifically, a probe microphone will be placed in the ear canal by an expert with headphones in situ to assess the precise level of amplification at every frequency and at different input levels. These measurements assess the frequency-level dependent gain that a given ear receives relative to the acoustic targets defined for a chosen fitting formula (i.e., NAL-NL2 [National Acoustic Laboratories for prescribing nonlinear gain]).
 
Participants in both groups will have baseline unaided Speech-In-Noise (SIN) objective assessment to gauge independent ability in these primary aspects of hearing.
 
Home Interval 2
 
Participants will return to their baseline environmental exposures for at least 14 days with ability to adjust settings within parameters to optimize their settings.
 
Clinic Visit 3
 
When participants return for the final clinic day, they will complete the IOI-HA survey, have final Real Ear measures with headphones in situ to assess changes after field adjustments, and participate in aided SIN testing.

--	--

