8.1.4.6. Speech-In-Noise

A healthcare provider will oversee speech-in-noise testing at Clinic Visit 2 (unaided), and at Clinic Visit 3 (aided).

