To assess the exploratory objectives, the Speech in Noise (SIN) test scores will be summarized descriptively for each assessment visit (baseline and final) for each of the two randomized groups (Self-Fit and Pro-Fit) along with corresponding 95% confidence intervals for the means based on the t-distribution. Additionally, a two-sided 95% confidence interval for the mean difference between groups of the within-subject differences will be reported. For the real ear measures testing, the REM output values (dB SPL) will be summarized descriptively from all available ears at each frequency and averaged across all frequencies separately for each of the two study arms (Self-Fit and Pro-Fit). The mean absolute difference (MAD) between the Self-Fit and NAL-NL2 targets and the MAD between the Pro-Fit and NAL-NL2 targets will also be computed at each frequency and averaged across all frequencies using all available ears.

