7.3. Significance Level

The primary hypothesis test will use a one-sided significance level of 0.025. Analyses of the exploratory objectives will use 95% confidence intervals. Multiple comparison corrections will not be used.

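### The Speech-in-Noise arm comparison uses unadjusted change scores; a linear model adjusting for the unaided score would usually give a narrower interval, at almost no cost

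*SAP*

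**What the plan says.** SAP 9.7 sets out the SIN testing: "Three different Speech in Noise (SIN) test lists will be administered at clinic visit 2 (unaided) and again at clinic visit 3 (aided"). The three list scores are averaged at each visit. The between-arm comparison follows: "Additionally, the mean difference between treatment groups of the within-subject differences". The same sentence defines the change and its interval: "within-subject differences (clinic visit 3 – clinic visit 2) will be reported along with the corresponding two-sided 95% confidence interval". Protocol 9.2 has the same comparison: "a two-sided 95% confidence interval for the mean difference between groups of the within-subject differences will be reported". Neither section names a covariate or a model.

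The unaided score is collected in both arms, and Protocol 2.3.1 treats it as a baseline: "Participants in both groups will have baseline unaided Speech-In-Noise (SIN) objective assessment". It is not a pre-randomization value. The same section places allocation at Clinic Visit 1 ("Following enrollment, participants will be randomly assigned into 2 independent groups (SF or PF")), and the unaided test comes at Clinic Visit 2, after the first fitting and Home Interval 1.

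On status, SAP 6.2 lists the SIN comparison among additional descriptive analyses, and SAP 7.3 says: "Analyses of the exploratory objectives will use 95% confidence intervals". Protocol 2.3.2 names two measures for the exploratory objective, Real Ear measures and SIN.

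**The concern.** Subtracting the unaided score imposes a slope of exactly 1 between aided and unaided performance. If the true slope differs from 1, the change score carries variance that a regression on the unaided score would remove. The unaided score is already in the database, so the precision is available for no extra data.

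What is at stake is the width of one interval. SIN has no hypothesis test, so that interval is the result a reader will use. It is also the only between-arm interval that SAP 9.7 describes: the Real Ear output and target-deviation values serve the same objective, but are summarized for each arm with no stated between-arm difference. Randomization is unstratified (SAP 7.2) and enrolment spans 15 to 60 dB HL (SAP 4), so some chance imbalance in unaided ability is to be expected, and the two estimators treat it differently.

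**Working it through.** **Inputs from the documents.** 1:1 allocation; a minimum of 90 usable data sets, so 90/2 = 45 per arm; 112 enrolled, so 56 per arm; two-sided 95% intervals; unadjusted change score. The documents state no SD, correlation, interval width or power for SIN, so there is no planned figure to reproduce.

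**Assumed inputs.** Within-arm correlation rho from 0.3 to 0.95, and ratio k of aided SD to unaided SD of 0.8, 1 or 1.25. The slope of aided on unaided score is b = rho × k. Widths are in units of the unaided SD, s0.

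**Variance per participant.**
- Change score: Vc = s0²(1 + k² − 2·rho·k)
- Adjusted model: Va = s0²·k²(1 − rho²)
- Difference: Vc − Va = s0²(1 − b)²

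In large samples the change score is therefore never the more precise of the two, and they tie only at b = 1. With equal SDs, Va/Vc = (1 + rho)/2.

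**Half-width of the 95% interval with n per arm.**
- Change score: t(0.975; 2n − 2) × √(2Vc/n)
- Adjusted model: t(0.975; 2n − 3) × √((2Va/n) × (1 + 1/(2n − 4)))

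The last factor is the small-sample price of estimating the slope.

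**One case in full: n = 45, k = 1, rho = 0.5.** Vc = 1 and Va = 0.75. Change score: 1.987 × √(2/45) = 1.987 × 0.2108 = 0.419. Adjusted: 1.988 × √(0.0444 × 0.75 × 1.0116) = 1.988 × 0.1836 = 0.365. The ratio is 0.871, or 13% narrower.

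**Results at 45 per arm** (ratio = adjusted width / change-score width):

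| rho | k = 0.8: ratio | k = 1: half-widths, change to adjusted | k = 1: ratio | k = 1.25: ratio |
|---|---|---|---|---|
| 0.3 | 0.713 | 0.496 to 0.402 | 0.811 | 0.891 |
| 0.5 | 0.760 | 0.419 to 0.365 | 0.871 | 0.951 |
| 0.7 | 0.797 | 0.325 to 0.301 | 0.927 | 0.996 |
| 0.8 | 0.805 | 0.265 to 0.253 | 0.954 | 1.006 |
| 0.9 | 0.784 | 0.187 to 0.184 | 0.980 | 0.980 |
| 0.95 | 0.725 | 0.132 to 0.132 | 0.993 | 0.907 |

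At 56 per arm the ratios differ by no more than about 0.002. The worst cell, 1.006, is k = 1.25 with rho = 0.8, where b = 1 and there is nothing to gain.

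**Simulation check** (equal SDs, 45 per arm, 4,000 trials per setting). The mean width ratios were 0.872, 0.927, 0.980 and 1.001 at rho 0.5, 0.7, 0.9 and 0.98. The adjusted interval was the narrower one in 99.9%, 98%, 77% and 37% of trials.

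**Chance imbalance.** If the arms differ by D in mean unaided score, the change score subtracts D and the adjusted model subtracts b·D, a gap of (1 − b)·D. At 45 per arm the standard error of D is √(2/45) = 0.211 s0. At an assumed slope of 0.6, an imbalance of one standard error moves the change-score estimate by 0.4 × 0.211 = 0.084 s0 relative to the adjusted one. The change score over-corrects only when b is below 1. At b = 1 the two agree, and above 1 it under-corrects (for example k = 1.25 and rho = 0.9 give b = 1.125).

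**The case against.** **The analysis is descriptive.** SIN has no margin, test, power claim or success rule, so no trial conclusion changes with this interval. This stands, and it limits the point to a minor one.

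**The change score matches the objective.** The exploratory objective is improvement in hearing, and aided minus unaided is each participant's improvement. This also stands, and is a good reason to keep the change-score difference in the report.

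**Adjustment brings an assumption of its own.** The unaided score follows randomization, fitting and 3 to 8 days of use. If assignment shifted it, the change score would still estimate the arm difference in aided-minus-unaided benefit. The adjusted estimate would equal that quantity only if the slope were 1. The objection is correct and the assumption must be stated. It does not defeat the proposal. The test is taken without the device, so an arm effect should be small, and the change score subtracts the same value. If the target is the arm difference in aided hearing, a shift d enters the change-score estimate as −d and the adjusted estimate as −b·d, which is less for slopes between 0 and 1.

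**The gain may be negligible.** Averaging three lists and enrolling across a wide hearing range could push the correlation up. With equal SDs, the gain is 2% at rho 0.9 and 1% at 0.95. The documents cannot settle this.

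A reader might infer that adjustment is never less precise. That is a large-sample result; at this size the interval can be slightly wider when the slope is near 1.

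**Conclusion.** The planned comparison is valid but usually less precise than the adjusted one. At about 45 per arm:
- Equal SDs: about 13%, 7%, 5% and 2% narrower at rho 0.5, 0.7, 0.8 and 0.9.
- Aided SD 0.8 of unaided: about 19% to 29% narrower for rho from 0.3 to 0.95.
- Aided SD 1.25 times unaided: between 11% narrower and 1% wider over the same range.

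All of these rest on assumed correlations and SD ratios, a common linear slope, and no material effect of arm on the unaided score.

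A reader might infer that the planned interval is biased or has the wrong coverage, or that the change score always over-corrects for imbalance. The documents support neither: randomization protects the planned estimator, and over-correction needs a slope below 1, on which they are silent. Nor does the point touch the non-inferiority conclusion, which rests on the IOI-HA score alone. This is a cheap improvement to an exploratory analysis.

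**What to change.** In SAP 9.7, and to match in Protocol 9.2:
- Estimate the SIN arm difference from a linear model of the Visit 3 aided average score on arm and the Visit 2 unaided average score, with its two-sided 95% confidence interval.
- Keep the between-arm difference in change as a descriptive row.
- State that the unaided score is measured after randomization and Home Interval 1, so the adjusted estimate assumes that arm has no material effect on it.

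The cost is a few lines of text and one regression, with no new data, visits or participants. The price is the assumption just stated, a common linear slope across arms, and at most about 1% in interval width if the slope is near 1. The model should be fixed before the data are seen, so that the choice between the two estimators cannot follow the results.

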9.8. Safety Analyses

All adverse events will be recorded throughout the entire study period, whether they are considered to be related to the study procedures or not. Signs and symptoms of each AE will be described in detail: date of event, description of event, severity, relationship to study procedures, action taken and outcome. Adverse events will be collected as spontaneously reported by the subjects.

Adverse events will be coded using MedDRA v24.1. The number of any adverse events and the number and percentage of subjects reporting each type of adverse event will be presented by preferred term. Multiple occurrences of the same event reported by the same subject will be counted only once.

Adverse event summaries (number of events and incidence) will be presented for:

- All adverse events
- Serious adverse events (SAEs)
- Study procedure related adverse events
- Severe adverse events

The intensity of an AE will be categorized as follows:

- Mild: Events that are transient, easily tolerated by the participant, and does not affect the participant's daily activities
- Moderate: Events that cause the participant discomfort and interrupts the participant's usual daily activities. May require treatment but not extended hospitalization for the participant.
- Severe: Events that are incapacitating, causing inability to do work or usual activities; signs and symptoms may require medical evaluation and/or treatment, and may require additional prolonged hospitalization

Causal relationship assessment to study procedures is required for purposes of reporting AEs. To promote consistency, the following guidelines should be taken into consideration along with good clinical and scientific judgment when determining the relationship of study procedures to an AE:

- Probably Related: There is a strong temporal relationship to the study or device, and an alternative etiology for the AE is unlikely.
- Possibly Related: The event is not readily explained by the participant's medical condition, concomitant therapy, or other causes, and there is a plausible temporal relationship between the event and participation in study procedures.

- Probably Not Related: An event, for which an alternative explanation is more likely (e.g., concomitant medications or ongoing medical conditions) or the temporal relationship to study procedures and/or exposure suggests that a causal relationship is unlikely.
- Not Related: An AE that does not follow a reasonable temporal sequence from participating in study procedures and/or that can reasonably be explained by other factors, such as underlying diseases, complications, concomitant drugs, and concurrent treatments.

Study procedure related events will include those events classified as possibly or probably related to the study procedure.

Action taken will be defined as:

- None;
- Study procedures interrupted;
- Study procedures stopped

Outcome will be defined as:

- Resolved;
- Ongoing or stabilized and followed by private healthcare provider;
- Lost to follow up

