7.3.3. Causal Relationship Assessment

The assessment of causal relationship to study procedures is required for the purposes of reporting AEs. When determining the relationship of study procedures to an AE, to promote consistency, the following guidelines should be taken into consideration, along with good clinical and scientific judgment:

The relationship of each AE to study procedure(s) will be assessed using the following categories:

Probably Related:	There is a strong temporal relationship to the study or device, and an alternative etiology for the AE is unlikely.
Possibly Related:	The event is not readily explained by the participant's medical condition, concomitant therapy, or other causes, and there is a plausible temporal relationship between the event and participation in study procedures.
Probably Not Related:	An event for which an alternative explanation is more likely (e.g., concomitant medications or ongoing medical conditions) or the temporal relationship to study procedures and/or exposure suggests that a causal relationship is unlikely.
Not Related:	An AE that does not follow a reasonable temporal sequence from participating in study procedures and/or that can reasonably be explained by other factors, such as underlying diseases, complications, concomitant drugs, and concurrent treatments.

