7.3.5. Unanticipated Adverse Device Effects

An Unanticipated Adverse Device Effect is defined as any serious adverse device effect on health or safety or any life-threatening problem or death caused by or associated with the device that was not previously identified in nature, severity, or degree of incidence in the investigational plan (including the protocol, the ICF, the PI's brochure, or other study-related documents).

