7.4. Reporting

7.4.1. Adverse Events

Throughout the entire study period, once participants have signed the ICF, the PI and/or designee(s) will evaluate participants at each study visit, record all AEs (whether or not they are considered to be related to the study procedures), and determine if any AEs are device- or study-related. Signs and symptoms of each AE should be described in detail and include approximate onset time and date, approximate offset time and date, description of event, severity, relationship to study procedures, action taken, outcome,

and (if applicable) the PI's opinion of the causal relationship between the event and the study procedures.

AEs will be collected as reported by participants and reported as observed by study staff. All AEs will be documented on the AE form and will be reported within 10 working days of learning of the event by Study Staff to the Sponsor. If deemed necessary by the Sponsor, the CRO or Study Staff will notify the Institutional Review Board (IRB).

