9.2. Data Analysis

In general, descriptive statistics (e.g., N, Mean, Std. Dev., Min, Max) for continuous data types and frequencies for categorical data types will be displayed. All analyses will be performed with SAS [REDACTED] and/or R [REDACTED]. Analysis results will be presented separately for each of the two randomized groups and overall as appropriate.

Subject accountability (number of enrolled, withdrawn (and reasons), and complete), demographic and baseline characteristics (i.e., age, sex at birth, race, ethnicity, height, weight, BMI, etc.) and medical history will all be summarized using the Full Analysis Set. Baseline ear measures (i.e., PTA, bone conduction, and tympanometry) will be summarized separately for each ear.

All adverse events will be summarized in terms of event type, severity, and relationship to device/study procedures. Serious adverse events will also be summarized. The overall incidence (number of study participants and number of events) will be presented as both frequency counts and percentages.

Details of the efficacy analyses including the primary endpoint and additional exploratory analyses are presented below.

The full analysis set will be used as the pivotal analysis set to test the primary endpoint hypothesis. The methodology and missing data mechanism assumptions will be described in the study Statistical Analysis Plan (SAP). The null hypothesis, H_0 , will be rejected and the Self-Fit group will be considered non-inferior to the Pro-Fit group if the one-sided p-value for this test is $p < 0.025$ or equivalently, if the one-sided upper 97.5% confidence bound for the difference (Pro-Fit – Self-Fit) of the two group means is no more than 3. The primary endpoint analysis will also be performed on the Per Protocol and Complete Cases Analysis Sets as supportive analyses.

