Table 14.2.1.3	Logistic Regression Analysis to Evaluate Probability of Missingness – Per Protocol Analysis Set
Table 14.2.1.4	Primary Endpoint Analysis of IOI-HA – Per Protocol Analysis Set
Table 14.2.1.5	Primary Endpoint Analysis of IOI-HA – Complete Cases Analysis Set
Table 14.2.1.6	IOI-HA Item Summary – Complete Cases Analysis Set
Table 14.2.2	QuickSIN Results– Complete Cases Analysis Set
Table 14.2.3.1.1	Real Ear Measures Summary at 50 dB SPL (Clinic Visit 2) – Complete Cases Analysis Set
Table 14.2.3.1.2	Real Ear Measures Summary at 50 dB SPL (Clinic Visit 3) – Complete Cases Analysis Set
Table 14.2.3.2.1	Real Ear Measures Summary at 65 dB SPL (Clinic Visit 2)– Complete Cases Analysis Set
Table 14.2.3.2.2	Real Ear Measures Summary at 65 dB SPL (Clinic Visit 3)– Complete Cases Analysis Set
Table 14.2.3.3.1	Real Ear Measures Summary at 80 dB SPL (Clinic Visit 2) – Complete Cases Analysis Set
Table 14.2.3.3.2	Real Ear Measures Summary at 80 dB SPL (Clinic Visit 3) – Complete Cases Analysis Set
Table 14.2.4.1	Mean Absolute Difference of Real Ear Measures from NAL-NL2 Targets at 50 dB SPL– Complete Cases Analysis Set
Table 14.2.4.2	Mean Absolute Difference of Real Ear Measures from NAL-NL2 Targets at 65 dB SPL
Table 14.2.4.3	Mean Absolute Difference of Real Ear Measures from NAL-NL2 Targets at 80 dB SPL

Table 14.3.1.1	Summary of Adverse Events – Full Analysis Set
Table 14.3.1.2	All Adverse Events Sorted Alphabetically – Full Analysis Set
Table 14.3.1.3	Serious Adverse Events – Full Analysis Set
Table 14.3.1.4	Adverse Events Possibly or Probably Related to Study Procedures – Full Analysis Set
Table 14.3.1.5	Adverse Events Rated Severe in Intensity – Full Analysis Set

List of Listings

Listing 16.2.1	Discontinued Patients
Listing 16.2.2.1	Protocol Deviations: Type and Description
Listing 16.2.2.2	Protocol Deviations: Severity and Actions Taken
Listing 16.2.4.1	Baseline Demographics
Listing 16.2.6.1	IOI-HA Responses
Listing 16.2.7.1	Adverse Events: Description and Timing
Listing 16.2.7.2	Adverse Events: Severity and Relationship
Listing 16.2.7.3	Adverse Events: Actions and Outcomes
Listing 16.2.9.1	Subject Eligibility and Enrollment
Listing 16.2.9.2	Perceived Hearing Loss Questionnaire
Listing 16.2.9.3	Subject Disposition
Listing 16.2.9.4	Medical History
Listing 16.2.9.5.1	Otoscopy Examination Results
Listing 16.2.9.5.2	Otoscopy Examination Additional Information
Listing 16.2.9.6	Clinical Visits Summary
Listing 16.2.9.7.1	Pure Tone Reference Audiometry (1)

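### The protocol calls for a device judgement on adverse events, but no separate device field or table is specified, and the SAP's once-only counting rule is not limited to subject counts

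*SAP*

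**What the plan says.** **Where the device is a separate question.** Protocol 7.4.1 requires the investigator to "determine if any AEs are device- or study-related". Protocol 7.3.5 defines an unanticipated adverse device effect as a serious effect "caused by or associated with the device that was not previously identified" in the study documents. Protocol 9.2 states: "All adverse events will be summarized in terms of event type, severity, and relationship to device/study procedures".

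**Where it is not.** The attributes to be recorded under Protocol 7.4.1 include "description of event, severity, relationship to study procedures, action taken, outcome", with no device relationship named. The only causality scale, in Protocol 7.3.3, opens with "The relationship of each AE to study procedure(s) will be assessed using the following categories", and SAP 9.8 repeats it. The SAP's only related-event definition is "Study procedure related events will include those events classified as possibly or probably related to the study procedure", and the only relatedness table in SAP section 13 is Table 14.3.1.4, "Adverse Events Possibly or Probably Related to Study Procedures".

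**Counting.** Protocol 9.2 asks for numbers of participants and of events. SAP 9.8 likewise promises event numbers alongside incidence, but also says: "Multiple occurrences of the same event reported by the same subject will be counted only once".

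**The concern.** The trial evaluates self-fitting hearing software for over-the-counter use (SAP 2.2). A safety summary for such a product should let the reader see which events were attributed to the headphones or software and which to clinic procedures that an ordinary user will not undergo. The contrast is real here. Participants wear the device over home intervals of 3 to 8 and 14 to 22 days (3 + 14 = 17 to 8 + 22 = 30 days in all), and they also have a probe microphone placed in the ear canal at two visits. On a single scale, an AE from either source can carry the same code.

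The judgement also matters for classification. Protocol 7.3.4 states that no adverse device effects are anticipated from the smartphone or headphones. A serious event judged to be associated with the device could therefore meet the definition in 7.3.5, subject to what the consent form and other study documents identify. If the device judgement is not recorded when the event occurs, it has to be reconstructed later.

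On counting, an effect that returns with repeated wear is informative because it returns. A rule that reduces repeats to one would hide that in the event column.

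**Working it through.** The documents state no AE figure to reproduce. The check is a comparison of texts plus one line of counting logic.

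**1. Relationship: what is asked for and what is specified**

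| Step | Protocol | SAP |
|---|---|---|
| Judgement | Device or study (7.4.1) | Study procedures (9.8) |
| Recorded attribute | Study procedures (7.4.1) | Study procedures (9.8) |
| Scale heading | Study procedures (7.3.3) | Study procedures (9.8) |
| Summary | Device/study procedures (9.2) | Study procedures (9.8; Table 14.3.1.4) |

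The device appears in the protocol's judgement and in its promised summary. It is missing from the attribute and the scale heading in between, and from every row of the SAP column. Of the five AE tables (14.3.1.1 to 14.3.1.5), none is titled for device relationship. Listing 16.2.7.2 gives severity and relationship, with no second attribution named.

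**2. The category wording, the same in both documents**

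- Probably Related: names the study or the device.
- Possibly Related: names participation in study procedures only.
- Probably Not Related: names study procedures and/or exposure, without saying exposure to what.
- Not Related: names study procedures.

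The device is thus named in one category of four. The scale does not leave the device out, but it does not separate it either, and an investigator with a possible device effect is not told whether Possibly Related applies.

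**3. The counting rule**

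Let subject *i*, among *m* subjects with a given event type, have it *k_i* times.

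- Subject count: *m*, with or without the rule.
- Event count with every occurrence counted: the sum of the *k_i*.
- Event count with the rule applied to events: *m*.
- Shortfall: the sum of (*k_i* − 1), which is zero only if nobody has a repeat.

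The rule changes nothing when applied to subjects and can only lower the total when applied to events. The documents give no *k_i* and no expected AE rate, so the shortfall cannot be sized.

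**The case against.** Several stronger conclusions are tempting, and the documents do not support them.

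- **That device-related AEs cannot be reported.** Protocol 7.4.1 requires the judgement, every AE is recorded, and the listings show description, timing, severity and relationship. With about 112 participants, case-level listings are readable. The AE form is not among the documents and may already hold a device field. Serious events go to the sponsor within 24 hours whatever their cause.
- **That the scale covers study procedures only.** Probably Related names the device. Protocol 3.2 and SAP 5 also place the home intervals, with daily device use, under study procedures, so Table 14.3.1.4 can include AEs from wear. The slash in Protocol 9.2 can be read as one combined category, which that table would supply.
- **That injury from wax removal is mixed with harm from the headphones.** Protocol 7.3.4 says that discomfort or injury from ear exams or wax removal is not an AE, and it also excludes complaints about headphone comfort and hearing symptoms. The overlap is narrower than it first appears.
- **That true event numbers are lost.** The once-only sentence follows a clause on the number and percentage of subjects, where it reads naturally as a subject rule, and the SAP then promises event numbers as a separate quantity.

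All of this stands, and it limits the point. Two things survive it. The combined reading of Protocol 9.2 does not settle 7.4.1, which puts device and study as alternatives, or 7.3.5, which turns on the device alone; and a listing is not a prespecified summary by arm. As for the counting sentence, the clause before it covers event numbers as well as subjects, and nothing in the wording limits it to the latter.

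**Conclusion.** The point holds in a limited form and is minor. First, the protocol asks for a device judgement and a summary that mentions the device, while the two documents specify one undifferentiated scale headed by study procedures, and the SAP has one relatedness table with the same limit. No separate device-relationship field or by-arm summary is specified. Second, the once-only sentence in SAP 9.8 is ambiguous; taken literally, it conflicts with the event numbers promised there and in Protocol 9.2.

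Neither part has a size that the documents allow to be stated. The conclusion assumes that the AE form, which is not available, follows the attribute list in Protocol 7.4.1. Only descriptive safety reporting is affected: no hypothesis, analysis set or element of the primary non-inferiority test changes.

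**What to change.** 1. In Protocol 7.3.3 and 7.4.1 and SAP 9.8, record two relationships for each AE on the same four-level scale: to the device (headphones or hearing software) and to study procedures. Word all four categories consistently for each. Limit this to occurrences that count as AEs under Protocol 7.3.4.
2. Add to SAP section 13 a by-arm table of AEs possibly or probably related to the device.
3. Replace the counting sentence in SAP 9.8 with: *For subject incidence, multiple occurrences of the same preferred term in a subject are counted once; for number of events, every occurrence is counted.*

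The cost is two attributions per AE instead of one, one more table and one reworded sentence. Reported event numbers may be higher than under the literal rule. If the AE form already holds a device field, the first change is to the documents only.
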